8 STUDY TREATMENTS

8.1 INVESTIGATIONAL MEDICINAL PRODUCT(S)

Avalglucosidase alfa will be supplied as a sterile, nonpyrogenic, lyophilized product in single-use vial containing approximately 100 mg of avalglucosidase alfa. Alglucosidase alfa is supplied as a sterile, nonpyrogenic, white to off-white, lyophilized cake or powder in a single-use vial containing 50 mg of alglucosidase alfa.

Quantity of vials required for each infusion will be calculated by IRT based on the patient's weight. The total amount of investigational product administered may be adjusted as needed to account for changes in body weight. Most recent body weight should be used for dose calculation; weight obtained at a previous infusion visit may be used for preparation of IMP, if obtained within a timeframe of 1 month. Each IV infusion will be administered in a step-wise manner. The rate will begin at a slow initial rate and will be gradually increased if there are no signs of IARs, until a maximum rate is reached. The infusion length will be dependent on the dose. For alglucosidase alfa only, the diluted solution should be filtered through a 0.2 – 0.22 micron, low protein-binding, in-line filter during administration to remove any visible particles. Specific details pertaining to the infusion volumes and rates as well as dose calculation, preparation, and administration of the investigational product can be found in the pharmacy manual.

Prior to each infusion, the patient should be assessed by the Investigator or appropriate designee (ie, qualified physician with the exception of patients who receive home infusion of alglucosidase alfa as outlined in [Section 8.9.1](#), conditions and instructions provided in [Section 8.9.2](#) for patients who receive home infusion of avalglucosidase alfa) to determine if the patient is free of acute illness and is clinically stable to receive the infusion. Infusions will be postponed (see [Section 8.7.1](#)) if the patient is acutely ill on the scheduled day of infusion. Any modification to the dose and/or frequency of dosing is not permitted unless it is due to an AE, in which case it is not a protocol violation, but the Investigator must consult with the Sponsor in the event of a dose change. The Sponsor will inform the DMC of any dose change related to AEs. For avalglucosidase alfa, no dose increase above the MTD of 20 mg/kg qow or 40 mg/kg qow (once determined) will be allowed for any patients.

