8.7.1 Treatment accountability and compliance

Administration of the IMP is performed in collaboration with qualified study personnel, and under the responsibility of the pharmacist or for Cohort 3 patients in the alglucosidase alfa arm already receiving home infusions, the Investigator or the Subinvestigator.

IMP accountability:

- Pharmacist or designee will record precisely the date, time of the drug administration and number of treatment units used for administration in the corresponding logs.
- The pharmacist or designee records the lot number of the treatment assigned by the central treatment allocation system/IRT at each visit in the appropriate log.
- The monitor assigned to the study will perform reconciliation.

The patient's compliance with the treatment regimen will be monitored in terms of the patient receiving the study drug infusion qow within a ± 7 -day window (or ± 3 -day window if the participant receives alglucosidase alfa qw in the treatment period as part of Cohort 3) from the scheduled infusion date based on V2 (Day 1). Missed, delayed, or incomplete infusions will be clearly documented. Missed doses of study treatment due to sickness, safety concerns, or for medical reasons are not protocol deviations, but must be documented for analysis and potential impact on the study results.

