11.4 STATISTICAL METHODS

11.4.1 Extent of study treatment exposure and compliance

The extent of study drug exposure will be assessed by the duration of study drug exposure, number of infusions, and amount of dose received. The extent of study drug exposure will be summarized in the safety population.

Duration of study drug exposure is defined below:

For the PAP

- Duration of IMP exposure is defined as the first dose date in the extension period (or 14 days after the last dose date in PAP if the patient is not continuing in extension period) minus (–) first dose date in the treatment period, regardless of unplanned intermittent discontinuations.

For the extension period,

- Duration of IMP exposure is defined as 14 days after the last dose in the extension period minus (–) the first dose date in the extension period, regardless of unplanned intermittent discontinuations. This is defined only for Cohort 3 alglucosidase alfa patients who are switched to avalglucosidase alfa and treated in the extension period.

For the overall treatment duration,

- Duration of avalglucosidase alfa total exposure is defined as 14 days after last avalglucosidase alfa dose in study minus (–) first avalglucosidase alfa dose date in the study. This is defined for all patients other than the Cohort 3 alglucosidase alfa patients.

The duration of IMP exposure will be summarized descriptively as a quantitative variable (number, mean, SD, median, minimum, and maximum), as well as categorical variable (eg, <2 months, 2-4 months, 4-6 months for the PAP).

The cumulative dose information for the considered period (PAP or overall treatment period) will be assessed by the total number of infusions received in the considered period, as well as total amount of IMP in mL (if this information is available from the database) received in the considered period. These data will be summarized descriptively.

For Cohorts 1 and 2, and Cohort 3 avalglucosidase alfa patients, both duration of IMP exposure and cumulative dose will be summarized for the PAP, as well as the overall treatment period. For Cohort 3 alglucosidase alfa patients, both duration of IMP exposure and cumulative dose will be summarized for the PAP; in addition, duration of IMP exposure will be summarized for the extension period after switching to avalglucosidase alfa.

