11.4.1.1 Compliance

A given administration will be considered noncompliant if the patient did not take the planned dose of treatment as required by the protocol. Compliance to the treatment regimen will be monitored by site personnel during the study.

Treatment compliance for the PAP and the extension period respectively will be summarized descriptively as quantitative variable using the safety population. The number and percentage of patients with noncompliance (missed 2 or more consecutive infusions not for safety cause, or missed $\geq 20\%$ of total doses in the treatment or extension period) will be provided.

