2.4.3 Extent of investigational medicinal product exposure and compliance

2.4.3.1 Extent of investigational medicinal product exposure

The extent of study drug exposure will be assessed by the duration of study drug exposure (weeks), number of infusions, amount of dose received and total duration of study drug exposure (patient \times years). The extent of study drug exposure will be summarized in the safety population.

Duration of study drug exposure is defined below:

For PAP,

- Duration of IMP exposure is defined as the first dose date in ETP (or 14 days after the last dose date in PAP if the patient is not continuing in ETP) minus (–) the first dose date in PAP, regardless of unplanned intermittent discontinuations.

For ETP,

- Duration of IMP exposure is defined as 14 days after last dose in ETP minus (–) the first dose date in ETP, regardless of unplanned intermittent discontinuations.

For the overall treatment duration,

- Duration of avalglucosidase alfa total exposure is defined as 14 days after last avalglucosidase alfa dose in study minus (–) first avalglucosidase alfa dose date in the study. This is defined for all patients other than the Cohort 3 alglucosidase alfa patients.

The duration of IMP exposure will be summarized descriptively as a continuous variable, as well as a categorical variable (e.g., <12 weeks, 12 to <24 weeks, \geq 24 weeks for PAP).

The cumulative dose information for the considered period (PAP, ETP, or the overall treatment period) will be assessed by the total number of infusions received in the considered period, as well as total amount of IMP in mL (if this information is available from the database) received in the considered period. These data will be summarized descriptively.

For Cohorts 1 and 2, and Cohort 3 avalglucosidase alfa patients, both duration of IMP exposure and cumulative dose will be summarized for PAP, ETP, as well as the overall treatment period.

For Cohort 3 alglucosidase alfa patients, both duration of IMP exposure and cumulative dose will be summarized for PAP; in addition, duration of IMP exposure will be summarized for ETP after switching to avalglucosidase alfa.

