2.4.3.2 Compliance

A given administration will be considered noncompliant if the patient did not take the planned dose of treatment as required by the protocol. Compliance to the treatment regimen will be monitored by site personnel during the study.

Treatment compliance for PAP will be analyzed using summary statistics in the safety population. Compliance is calculated as the total amount of drug actually taken by a patient divided by the total amount of drug expected to be taken multiplied by 100. The number and percentage of patients with noncompliance (missed 2 or more consecutive infusions, or missed \geq 20% of total doses in the treatment or extension period) will be provided.

Treatment compliance for ETP and overall study period will be summarized similarly.

Additional dose related non-compliance will be summarized as protocol deviations.

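### Cumulative dose is tabulated in mL rather than mg/kg, and the SAP non-compliance rule omits the protocol's exclusion for infusions missed for safety

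*SAP*

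**What the plan says.** **Exposure.** SAP 2.4.3.1 says exposure will be assessed by duration, "number of infusions, amount of dose received and total duration of study drug exposure". When it defines cumulative dose, it names two quantities only: the number of infusions, "as well as total amount of IMP in mL (if this information is available from the database) received in the considered period". Protocol 11.4.1 uses the same definition: "total amount of IMP in mL (if this information is available from the database) received in the considered period".

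The avalglucosidase alfa dose levels are in mg/kg (protocol 8.1.1). The Cohort 3 comparator is each child's own stable alglucosidase alfa dose, given weekly or every other week. Protocol 8.1 supplies avalglucosidase alfa in a "single-use vial containing approximately 100 mg of avalglucosidase alfa" and alglucosidase alfa in a 50 mg vial. It leaves infusion volumes to the pharmacy manual.

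**Compliance.** SAP 2.4.3.2 plans a percentage: "Compliance is calculated as the total amount of drug actually taken by a patient divided by the total amount of drug expected to be taken", times 100. It then plans a count: "The number and percentage of patients with noncompliance (missed 2 or more consecutive infusions, or missed" at least 20% of doses in the period). Protocol 11.4.1.1 has the same two-part rule, but its first part reads "missed 2 or more consecutive infusions not for safety cause". Its 20% part carries no such exclusion. Protocol 8.7.1 adds: "Missed doses of study treatment due to sickness, safety concerns, or for medical reasons are not protocol deviations", although they must be documented for analysis.

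**The concern.** This is an ascending-dose study whose primary objective is safety. A reader of the exposure tables will want two things: the dose per kilogram each group received, and how much dosing was withheld because of toxicity.

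On the first, neither quantity defined for cumulative dose is weight-based. This matters most in two places. One is the Cohort 3 control arm, where the dose is individual and no exposure table would show it. The other is the overall avalglucosidase alfa period, where SAP 2.4.4 groups safety results by initial planned dose although Cohort 1 patients may be escalated in the extension (protocol 8.1.2).

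On the second, protocol 10.3.1 stops dosing for certain adverse events pending review by the data monitoring committee, so safety holds are foreseen. Under the SAP rule, such a hold can enter the same count as infusions missed for unrelated reasons, and no table is named that separates them.

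**Working it through.** **1. Planned infusions.** Every-other-week count = (last week − first week)/2 + 1.
- Weeks 1 to 25: (25 − 1)/2 + 1 = 13, matching protocol 8.1.1.
- Weeks 27 to 145: (145 − 27)/2 + 1 = 60, matching protocol 8.1.2.
- Weekly alglucosidase alfa, Weeks 1 to 25: 25, assuming one infusion every week (the documents give no count).

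**2. Does mL identify the dose level?** Cumulative mg = dose × weight × 13. Body weights are assumptions.

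| Assumed weight | 20 mg/kg | 40 mg/kg |
|---|---|---|
| 10 kg | 2,600 mg | 5,200 mg |
| 20 kg | 5,200 mg | 10,400 mg |
| 40 kg | 10,400 mg | 20,800 mg |

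A 20 kg child at 20 mg/kg and a 10 kg child at 40 mg/kg both receive 5,200 mg. At one fixed concentration their total mL is the same. Across these weights the total varies fourfold within a dose level, against twofold between dose levels. The concentration is not in the documents, so mL cannot be converted to mg/kg from them.

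**3. Does infusion count identify it?** No. The count is 13 at both 20 and 40 mg/kg, and about 25 for a weekly comparator patient whatever the mg/kg.

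**4. What the compliance percentage carries.** It is relative, so full dosing at 20 and at 40 mg/kg both read 100%.
- 2 of 13 missed: 11/13 = 84.6%.
- 3 of 13 missed: 10/13 = 76.9%.
- Dose lowered from 40 to 20 mg/kg after infusion 6 (a direction of change that SAP 2.2 anticipates), with the original dose kept as expected: (6 × 40 + 7 × 20)/(13 × 40) = 380/520 = 73.1%.
- The same patient with the expected amount reset to the lower dose: 380/380 = 100%.

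The SAP does not say which expected amount applies after a dose change.

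**5. Where the two non-compliance rules differ.** Take a patient whose missed infusions are all for safety, with at least two in a row. The SAP flags this patient. The protocol does so only once the total reaches 20%, so the rules differ from 2 missed up to one below that threshold.

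| Period | Planned | Fewest missed that reach 20% | Rules differ at |
|---|---|---|---|
| Treatment period, every other week | 13 | 3 (23.1%) | 2 (15.4%) |
| Treatment period, weekly (assumed) | 25 | 5 (20.0%) | 2 to 4 (8.0% to 16.0%) |
| Weeks 27 to 145 | 60 | 12 (20.0%) | 2 to 11 (3.3% to 18.3%) |

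A single missed infusion in the treatment period is flagged by neither document. At or above the threshold, both flag the patient whatever the cause.

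**6. Weight of one patient.** Cohort 3 randomises at least 10 patients 1:1, so about 5 per arm: 1/5 = 20 percentage points.

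**The case against.** The strongest reply is that other planned outputs already show much of this.
- The compliance percentage adjusts for weight, product and frequency.
- SAP 2.2 plans counts and a listing of patients whose dose was raised or lowered.
- Protocol 11.4.2.1 plans adverse event listings with action taken on treatment, which is workable in about 20 patients.
- SAP 2.4.4.1 tabulates events leading to permanent discontinuation.
- Tables for the primary period are split by cohort and arm, so the column heading already separates 20 from 40 mg/kg in Cohorts 1 and 2.

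All of this stands. A reader might infer that the tables cannot show the dose received or tolerated, and the documents do not support that. What remains is that none of these outputs gives mg/kg received, describes the comparator's dose, or tabulates withheld infusions by reason.

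Three further inferences also go too far. The use of mL is not an SAP departure, because the protocol has the same unit. Not every child held for safety is mislabelled: one missed infusion triggers neither rule, and at 20% or more the protocol applies the same label. Nor does SAP 2.4.3.2 say that doses withheld for safety become protocol deviations. It sends additional dose-related non-compliance to deviations without repeating the carve-out in protocol 8.7.1, which leaves the point unclear rather than contradicted.

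**Conclusion.** Both parts hold in limited form.

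The mL definition, shared by both documents, leaves the exposure tables without a weight-based dose. The size of the distortion depends on body weights and concentrations that the documents do not give. The equal-mL example assumes 10 kg and 20 kg children and one concentration.

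The compliance rule is a conflict between the SAP and the protocol. It is confined to exactly 2 of 13 in the every-other-week treatment period, 2 to 11 of 60 in Weeks 27 to 145, and 2 to 4 of 25 for weekly dosing if 25 infusions are planned. The likely cause is version lag. SAP 1.5 cites the protocol dated 27 July 2018, and the amendment history shows that the protocol's compliance text was updated later, in amended protocol 02. SAP 1.5 and 1.6 do not list the omission as a deliberate change.

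The primary adverse event analysis does not depend on either part. Both affect how exposure and tolerability are described.

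**What to change.** 1. In SAP 2.4.3.1 and protocol 11.4.1, replace mL with actual mg/kg per infusion, cumulative mg and cumulative mg/kg, using the weight applied at each infusion. Present these by cohort, arm and dose level.
2. In SAP 2.4.3.2, define the expected amount after a dose change.
3. Restore the safety exclusion in the SAP's consecutive-infusion rule so that it agrees with protocol 11.4.1.1 and 8.7.1. State in both documents whether the exclusion also covers the 20% part. Restoring the phrase alone leaves a child held for 3 of 13 infusions flagged as non-compliant.
4. Tabulate missed, reduced or interrupted infusions by reason (adverse event or safety, versus other).

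The cost is wording in two documents and one derived dataset. The compliance formula already needs actual and expected drug amounts, body weight is collected monthly (protocol 9.1.1.6), and missed, delayed or incomplete infusions must already be documented (protocol 8.7.1). There is no added patient burden. If administered mg is not stored directly, it would have to be derived from volume and concentration using the pharmacy manual.

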2.4.3.2 Compliance

A given administration will be considered noncompliant if the patient did not take the planned dose of treatment as required by the protocol. Compliance to the treatment regimen will be monitored by site personnel during the study.

Treatment compliance for PAP will be analyzed using summary statistics in the safety population. Compliance is calculated as the total amount of drug actually taken by a patient divided by the total amount of drug expected to be taken multiplied by 100. The number and percentage of patients with noncompliance (missed 2 or more consecutive infusions, or missed \geq 20% of total doses in the treatment or extension period) will be provided.

Treatment compliance for ETP and overall study period will be summarized similarly.

Additional dose related non-compliance will be summarized as protocol deviations.

2.4.4 Analyses of safety data

In general, for PAP, the summary of safety results will be presented by study cohort and treatment arm. For the overall avalglucosidase alfa treatment period, the summary of safety results will be presented by initial planned dose levels among avalglucosidase alfa patients. For Cohort 3 alglucosidase alfa patients, the summary of safety results for ETP will be presented in separate tables.

In the PAP analysis, the safety analyses will be carried out with patients by the actual treatment received, irrespective of the treatment the patient has been randomized to. The actual treatment received is defined as:

- avalglucosidase alfa if the patient receives at least one infusion with this drug in PAP;
- alglucosidase alfa if the patient only receives alglucosidase alfa in PAP.

In the ETP analysis and/or overall evaluation of avalglucosidase alfa safety, the safety analyses will be carried out by the following 3 groups:

- AVAL/AVAL in ETP includes data in ETP among patients who received avalglucosidase alfa in PAP and ETP;
- ALGLU/AVAL in ETP includes data in ETP among patients who received alglucosidase alfa in PAP and received avalglucosidase alfa in ETP;
- AVAL/AVAL and ALGLU/AVAL in overall avalglucosidase alfa treatment period includes data in PAP and/or ETP among patients who received avalglucosidase alfa in that period.

General rules

All safety analyses will be performed on the safety population as defined in [Section 2.3.1](#), unless otherwise specified, using the following common rules:

- The safety baseline value is defined the same as the baseline definition in [Section 2.1.1](#).
- The potentially clinically significant abnormality (PCSA) values are defined as abnormal values considered medically important by the Sponsor according to predefined criteria/thresholds based on literature review and defined by the Sponsor for clinical laboratory tests, vital signs, and ECG (PCSA version dated January 2014 [[Appendix B](#)]).
 - PCSA criteria will determine which patients had at least 1 PCSA during the treatment epoch (for PAP and ETP respectively), taking into account all evaluations performed during this period, including nonscheduled or repeated evaluations.
 - The number of all such patients will be the numerator for the on-treatment PCSA percentage; the denominator will be the number of patients assessed for that given parameter in the treatment epoch by treatment group on the safety population.
- For the overall evaluation of avalglucosidase alfa safety, selected analysis will be repeated by dose levels among avalglucosidase alfa patients
- The analysis of the safety variables will be essentially descriptive and no inferential testing is planned.

